## **11 DATA MANAGEMENT**

### **11.1 Data Collection and management**

All data for an individual patient will be collected by the CI or designee and recorded in source documents/electronic case report form (CRF) for the study. For routinely collected clinical data the NHS record will be the source document. Patient identification on the CRF will be through their unique trial identifier, allocated at the time of randomisation. Data will be collected and recorded on the electronic CRF by the CI or designee as per the CRF submission guidelines. Following the entry of patient data into the study database, the data will be processed as per the CTU Standard Operating Procedures (SOPs) and the study specific Data Management Plan (DMP). Data queries will be generated electronically for site staff to clarify data or request missing information. The designated site staff will be required to respond to these queries. All queries will be responded to/resolved within the study database and amended in the study database.

#### 11.2 Data storage

All documentation and trial records will be stored in conformance with the applicable regulatory requirements. Access to stored information will be restricted to authorised personnel. The trial master file will be managed according to Sponsor SOP.

#### 11.3 Data archiving

Trial documentation and data will be archived after completion of the trial in keeping with the applicable regulatory requirements.

## **12 PHARMACOVIGILANCE**

## **12.1 Definition of Adverse Events**

The EU Clinical Trials Directive 2001/20 provides the definitions given in table 3

Term	Definition
Adverse Event (AE)	Any untoward medical occurrence in a participant to whom a medicinal product has been administered including occurrences which are not necessarily caused by or related to that product.
Adverse Reaction (AR)	Any untoward and unintended response in a participant to an investigational medicinal product, which is related to any dose administered to that participant.
Unexpected Adverse Reaction (UAR)	An adverse reaction the nature and severity of which is not consistent with the Reference Safety Information.
Serious Adverse Event (SAE) Serious Adverse Reaction (SAR)	An adverse event or adverse reaction that: results in death, is life-threatening, requires hospitalisation or prolongation of existing hospitalisation, results in persistent or significant disability or incapacity, consists of a congenital anomaly or birth defect, or any other important medical event(s) that carries a real, not hypothetical, risk of one of the outcomes above.
Suspected Serious Adverse Reaction (SSAR)	12.1.0.1 Any adverse reaction that is classed in nature as serious and is consistent with the Reference Safety Information (RSI)
Suspected Unexpected Serious Adverse Reaction (SUSAR)	12.1.0.2 Any adverse reaction that is classed in nature as serious and is not consistent with the Reference Safety Information (RSI)

Table 3: Terms and Definitions for	r Adverse Events
------------------------------------	------------------

Hospitalisation is defined as an inpatient admission regardless of length of stay, even if the hospitalisation is a precautionary measure for continued observation.

## **12.2 Eliciting Adverse Event Information**

The CI or designee will record all directly observed AEs and all AEs spontaneously reported by the patient. In addition the patient will be asked about AEs at each visit following initiation of treatment.

## 12.3 Assessment of Seriousness

The CI or designee should make an assessment of seriousness. This is an adverse event that:

- Results in death
- Is life-threatening
- Requires hospitalisation or prolongation of existing hospitalisation
- Results in persistent or significant disability or incapacity
- Consists of a congenital anomaly or birth defect

• Is any other important medical event(s) that carries a real, not hypothetical, risk of one of the outcomes above

## **12.4 Assessment of Causality**

Adverse Events (AE) will be clinically assessed by the CI or designee for causality based on the available information, i.e. the relationship of the AE to the study drug. Causality assessment decisions must be made by a medically qualified doctor. For the purposes of this trial the causality should be assessed using the categories below.

- **Not related**: Temporal relationship of the onset of the event, relative to administration of the product, is not reasonable or another cause can by itself explain the occurrence of the event.
- **Unlikely**: Temporal relationship of the onset of the event, relative to administration of the product, is likely to have another cause which can by itself explain the occurrence of the event.
- **Possibly**\*: Temporal relationship of the onset of the event, relative to administration of the product, but the event could have been due to another, equally likely cause.
- **Probably**\*: Temporal relationship of the onset of the event, relative to administration of the product, is reasonable and the event is more likely explained by the product than any other cause.
- **Definitely**\*: Temporal relationship of the onset, relative to administration of the product, is reasonable and there is no other cause to explain the event, or a re-challenge (if feasible) is positive.

\*Where an event is assessed as possibly, probably or definitely related to the study drug the event is an AR.

### 12.5 Assessment of Severity

The CI or designee should make an assessment of severity for each AE according to the following categories:

• Mild: A reaction that is easily tolerated by the trial participant, causing minimal discomfort and not interfering with every day activities.

- Moderate: A reaction that is sufficiently discomforting to interfere with normal everyday activities.
- Severe: A reaction that prevents normal everyday activities.
- Life Threatening: A reaction that has life threatening consequences; urgent intervention indicated.
- Death: A reaction that results in death.

### 12.6 Assessment of Expectedness

The sponsor is required to make an assessment of expectedness and this is delegated to the CI or designee. The CI or designee is required to make an assessment of expectedness of any ARs based on the relevant Reference Safety Information (RSI).

The reference safety information for this study is the version of the Summary of Product Characteristics (SPC) for Valaciclovir (section 4.8 undesirable effects) as approved by the Medicines and Healthcare Products regulatory Agency.

Adverse reactions may be classed as either:

• Expected: The AR is consistent with the toxicity of the study drug listed in the SPC.

• Unexpected: The AR is not consistent with the toxicity in the SPC.

An AR may be described as 'unexpected' if it has occurred with greater frequency or severity that might otherwise have been expected.

### **12.7 Adverse Event Reporting Period**

The AE reporting period for this trial begins on enrolment into the trial and ends 28 days following the administration of the study drug. All AEs assessed as possibly, probably or definitely related to the study drug and all SAEs that occur during this time will be followed until they are resolved or are clearly determined to be due to a patient's stable or chronic condition or intercurrent illness(es).

#### 12.8 Adverse Event Reporting

Adverse events (AEs) associated with the patient's underlying medical condition should not be reported. However if the clinician responsible for the patients care determines that the patients change in health is related to the trial this should be reported. AEs that are not related to the underlying medical condition should be recorded within the CRF. The investigator should attempt to establish a diagnosis based on the subjects signs and symptoms and if possible record the diagnosis in the CRF as opposed to reporting the individual symptoms. All AEs should be treated appropriately and the action taken should be recorded in the CRF. Once an AE is detected it should be followed up until resolution or stabilisation, or the events are otherwise explained and the outcome recorded in the CRF.

An adverse reaction (AR) (i.e. an AE which is related to the administration of the study drug must be reported on the AE Form within the CRF. An unexpected adverse reaction (UAR) is an AE which is related to administration of the study drug and that is unexpected, in that it has not been previously reported in the approved RSI All UARs must be reported on the AE form within the CRF.

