### **Rationale for the Dose**

This is the first trial of valaciclovir in COPD. Previous studies which have used this drug to suppress Epstein-Barr virus in oral hairy leukoplakia and infectious mononucleosis have used a dose of 1 gram three times daily . Because of this precedent, this study will use the same dose.

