### **12.9 Serious Adverse Event Reporting**

A Serious Adverse Event (SAE) is defined as an AE that fulfils one or more of the criteria for seriousness as defined in section 12.3. A serious adverse reaction (SAR) is a SAE which is related to the administration of the study drug. Suspected unexpected serious adverse reactions (SUSARs) are SAEs that are considered to be caused by the study drug and are unexpected, i.e. their nature or severity is not consistent with the RSI.

If a SAE occurs, reporting will follow the regulatory requirements as appropriate and all SUSARs will be the subject of expedited reporting.

SAEs should be reported using the Serious Adverse Event Report Form to the Sponsor within 24 hours of becoming aware of the event using the dedicated email address [contact]. Information not available at the time of the initial report should be documented on a follow-up SAE Report Form and submitted to the Sponsor. The SAE Form and any follow up report should also be submitted to the NICTU at the dedicated email address [contact].

The Chief Investigator or designee is responsible for reporting SAEs to the Sponsor, ethics committee and MHRA within the required time lines as per the regulatory requirements.

The CI or designee should contact the Sponsor immediately if the decision is taken that a SAR is a SUSAR using the dedicated email address, [contact].

For fatal or life-threatening SUSARs (7 day reporting), the Sponsor in collaboration with the CI will submit the SUSAR report as soon as possible but, within 7 calendar days of becoming aware of the event.

For non-fatal or life-threatening SUSARs (15 day reporting), the Sponsor in collaboration with the CI will submit the SUSAR as soon as possible but within 15 calendar days of becoming aware of the event.

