### 8.5 Toxicity/ Symptoms

- AEs, no.events (%) by treatment arm, no. patients(%) by treatment arm, Risk ratio with 95% CI
  - ARs, no.events (%) by treatment arm, no. patients(%) by treatment arm, Risk ratio with 95% CI
  - SAEs, no. events (%) by treatment arm, no. patients (%) by treatment arm, Risk ratio with 95% CI
  - SARs, no. events (%) by treatment arm, no. patients (%) by treatment arm, Risk ratio with 95% CI
  - UARs, no. events (%) by treatment arm, no. patients (%) by treatment arm, Risk ratio with 95% CI
  - SUSARs, no. events (%) by treatment arm, no. patients (%) by treatment arm, Risk ratio with 95% CI
  - Fatal AEs/SAEs, no. events (%) by treatment arm, no. patients (%) by treatment arm, Risk ratio with 95% CI
  - Safety bloods, mean(SD) by treatment arm at baseline and week 8
- AEs, ARs, SAEs, SARs, UARs and SUSARs will also be presented by system organ class.

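### Protocol 12.8 keeps events linked to the underlying condition off the CRF, contradicting 12.2 and 12.4, so some possibly drug-related, COPD-like events can be missing from the AE and AR comparison

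*Protocol*

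**What the plan says.** Protocol 12.8 opens with three sentences that together set a filter:

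- The exclusion: "Adverse events (AEs) associated with the patient's underlying medical condition should not be reported".
- An exception: "However if the clinician responsible for the patients care determines that the patients change in health is related to the trial this should be reported".
- What goes on the form: "AEs that are not related to the underlying medical condition should be recorded within the CRF".

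The same section later requires that an adverse reaction, meaning an AE "related to the administration of the study drug must be reported on the AE Form within the CRF".

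Other sections set no such filter. Protocol 12.2 says: "The CI or designee will record all directly observed AEs and all AEs spontaneously reported by the patient". The AE definition in 12.1 includes occurrences that need not be caused by the product. Protocol 12.4 has AEs assessed for causality on a five-step scale, with the decision made by a medically qualified doctor. Possibly, probably and definitely related events are all adverse reactions, and *possibly* covers events for which another cause is equally likely.

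For serious events, 12.9 says: "A Serious Adverse Event (SAE) is defined as an AE that fulfils one or more of the criteria for seriousness". It requires an SAE report to the sponsor within 24 hours and states no exemption for underlying disease. Protocol 12.7 has all SAEs in the reporting period followed up.

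The primary safety outcome is the incidence of serious adverse reactions (Protocol 5.3.1, SAP 7.1). SAP 8.5 compares AEs, ARs, SAEs and SARs by arm with risk ratios, and adds: "AEs, ARs, SAEs, SARs, UARs and SUSARs will also be presented by system organ class".

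**The concern.** Evaluating the safety of valaciclovir in COPD is the first primary objective (Protocol 4.3), and the dose rationale notes: "This is the first trial of valaciclovir in COPD". Respiratory worsening is the kind of event most readily put down to COPD, so it is also the kind most exposed to a rule that leaves out events associated with the underlying condition.

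If the drug changed the frequency of such events in either direction, a safety table built from the filtered CRF would understate the difference. The DMEC, whose main function under Protocol 15.2 is to check safety from adverse events, would see the same filtered data. There is also less other information to fall back on, because lung function and research blood sampling were dropped and the remaining visits moved to telephone.

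The term *underlying medical condition* is not defined, so how much is filtered may differ between assessors.

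**Working it through.** The documents give no AE rates, so there is no plan figure to reproduce. The check is a comparison of the sections, followed by an illustration of the mechanism.

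**Step 1: follow one event through the text.** Take a non-serious respiratory worsening on treatment that a doctor would consider equally likely to be due to COPD or to the study drug.

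| Section | What happens to the event |
|---|---|
| 12.2 | Recorded |
| 12.4 | Graded *possibly* related, hence an adverse reaction |
| 12.8, later text on reactions | Must go on the AE form |
| 12.8, first and third sentences | Can be treated as associated with the underlying condition and left off the CRF |
| 12.8, second sentence | Brought back only if the treating clinician determines that it is related to the trial |

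The result depends on which rule is applied first, and the protocol does not say. If 12.4 comes first, the event is a reaction and must be reported. If 12.8 comes first, it may never be graded. The exception does not settle this: it does not refer to the 12.4 categories, and *determines that it is related* reads as a higher bar than *possibly*.

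**Step 2: serious events.** Two provisions suggest that SAEs escape the filter: 24-hour reporting in 12.9 without a disease exemption, and follow-up of all SAEs in 12.7. One provision leaves doubt: an SAE is defined as an AE, and no sentence limits 12.8 to non-serious events.

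**Step 3: illustration of the effect on the AE risk ratio.** The only input from the documents is 44 patients per arm (Protocol 13.1). All rates are assumptions: non-COPD AEs in 30% of each arm, independent of COPD-like AEs, with a share q of COPD-like AEs recorded, equal in both arms because the filter is applied blind.

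Recorded any-AE risk = 1 − (1 − 0.30) × (1 − q × COPD-like risk)

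With COPD-like AEs in 20% (placebo) and 40% (valaciclovir):

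- q = 1: placebo 1 − 0.70 × 0.80 = 0.44; valaciclovir 1 − 0.70 × 0.60 = 0.58; RR = 0.58/0.44 = 1.32 (19.4 and 25.5 patients expected of 44).
- q = 0.5: placebo 1 − 0.70 × 0.90 = 0.37; valaciclovir 1 − 0.70 × 0.80 = 0.44; RR = 0.44/0.37 = 1.19 (16.3 and 19.4 patients).
- q = 0: 0.30 in both arms; RR = 1.00 (13.2 patients each).

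| Assumed COPD-like risk, placebo v valaciclovir | RR, all recorded | RR, half recorded | RR, none recorded |
|---|---|---|---|
| 10% v 30% | 0.51/0.37 = 1.38 | 0.405/0.335 = 1.21 | 1.00 |
| 20% v 40% | 0.58/0.44 = 1.32 | 0.44/0.37 = 1.19 | 1.00 |
| 20% v 50% | 0.65/0.44 = 1.48 | 0.475/0.37 = 1.28 | 1.00 |

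The true share recorded cannot be found from the documents. Even with full recording, Fisher's exact test at 44 per arm has power of only 18% to 41% in these scenarios. What is at stake is therefore the estimate and the signal visible to the DMEC, more than a significance test.

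**The case against.** The strongest reply is that 12.8 should be read as a whole and alongside its neighbours.

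- **Relatedness is considered.** The sentence after the exclusion restores events that the treating clinician judges related to the trial, and adverse reactions must be reported. A reader might infer that COPD-like events are discarded before anyone considers the drug; the text does not support that. What stands is that this judgement is informal and outside the 12.4 scale.
- **Serious events appear to be captured.** Besides 12.9, 12.7 ends follow-up of SAEs when they resolve or are clearly due to a stable or chronic condition. That presupposes an SAE is captured first and attributed to chronic disease later. Any inpatient admission counts as hospitalisation under 12.1. A reader might infer that a COPD admission can never become a SAR, or that the SAE table could be emptied. That is one possible reading, and not the most natural one.
- **Exacerbations are not lost.** They are documented at each contact through week 12 and compared by arm as an exploratory outcome (SAP 8.4). This stands. The planned analysis, however, is a mean count with no causality or seriousness, and it sits outside the safety table.
- **Disease-related events add noise** and should balance across randomised arms. That holds only if the drug does not affect them, which is the question being asked.

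**Conclusion.** The concern holds for non-serious events. Section 12.8 conflicts with 12.2 and 12.4, and a site that follows it can leave out COPD-like events that 12.4 would class as adverse reactions. The AE and AR risk ratios in SAP 8.5 and the DMEC's review can then be incomplete for the events most relevant to safety in COPD. A blinded filter with an equal share in each arm would dilute a real difference in any-AE risk, not create one.

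For serious events, and so for the primary safety outcome, the documents are ambiguous. They lean towards full capture, and loss of SARs is not established.

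The size is unknown. The movement of the risk ratio from between 1.32 and 1.48 down to 1.00 rests wholly on assumed rates and, at the extreme, on no COPD-like event being recorded. It shows the direction and mechanism only.

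**What to change.** 1. **Protocol 12.8.** Replace the first three sentences together. Removing only the first would leave the filter in the third and strand the exception. Suggested text: *All AEs are recorded on the CRF whatever their presumed cause, including events thought to be due to COPD or another existing condition, and each is assessed for causality under 12.4.* This brings 12.8 into line with 12.2 and 12.4.
2. **Protocol 12.8 or 12.9.** Add: *Nothing in 12.8 limits the reporting of SAEs under 12.9.*
3. **SAP 8.5.** Present the exacerbations already documented from baseline to week 12 by arm beside the AE table, and COPD admissions by arm as captured through the SAE form. On-trial admissions should come from that form: the SAP summarises hospitalised exacerbations only as baseline history.

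The cost is a short protocol amendment, a few table rows, some extra CRF entries and a noisier AE listing. The protocol's amendment for the lockdown refers to remaining visits, so the trial was already under way. If the rule changes mid-trial, record the date so that events under the two recording rules can be told apart. For the period under the present wording, the report should state that AE and AR counts may omit events attributed to the underlying condition.

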### **12.9 Serious Adverse Event Reporting**

A Serious Adverse Event (SAE) is defined as an AE that fulfils one or more of the criteria for seriousness as defined in section 12.3. A serious adverse reaction (SAR) is a SAE which is related to the administration of the study drug. Suspected unexpected serious adverse reactions (SUSARs) are SAEs that are considered to be caused by the study drug and are unexpected, i.e. their nature or severity is not consistent with the RSI.

If a SAE occurs, reporting will follow the regulatory requirements as appropriate and all SUSARs will be the subject of expedited reporting.

SAEs should be reported using the Serious Adverse Event Report Form to the Sponsor within 24 hours of becoming aware of the event using the dedicated email address [contact]. Information not available at the time of the initial report should be documented on a follow-up SAE Report Form and submitted to the Sponsor. The SAE Form and any follow up report should also be submitted to the NICTU at the dedicated email address [contact].

The Chief Investigator or designee is responsible for reporting SAEs to the Sponsor, ethics committee and MHRA within the required time lines as per the regulatory requirements.

The CI or designee should contact the Sponsor immediately if the decision is taken that a SAR is a SUSAR using the dedicated email address, [contact].

For fatal or life-threatening SUSARs (7 day reporting), the Sponsor in collaboration with the CI will submit the SUSAR report as soon as possible but, within 7 calendar days of becoming aware of the event.

For non-fatal or life-threatening SUSARs (15 day reporting), the Sponsor in collaboration with the CI will submit the SUSAR as soon as possible but within 15 calendar days of becoming aware of the event.

### 12.10 Recording and Reporting of Urgent Safety Measures

If the CI becomes aware of information that necessitates an immediate change in study procedure to protect clinical trial participants from any immediate hazard, they can implement this immediately prior to approval by REC/MHRA. The CI should phone the Clinical Trials Unit at the MHRA and discuss the issue with a medical assessor once an urgent safety measure is taken. Urgent safety measures should be reported to the Sponsor immediately, using the dedicated email address, [contact]

The MHRA and the main REC will be informed in writing providing full details of the measures taken, the reason for them, the medical assessor contacted and any supporting documentation within 3 days.

Details of the urgent safety measure should also be submitted to the NICTU at the dedicated email address [contact].

## 12.11 Pregnancy Reporting

Pregnancy is not considered an AE or a SAE however, an abnormal outcome would be. Therefore, the CI or designee must collect pregnancy information for female participants, and for females who become pregnant while their partners are participating in the trial. Consent should be obtained to follow up the pregnancy from the female partners of male participants.

The pregnancy reporting period for the trial is from the commencement of the study drug until 28 days post administration of the final dose of study drug. The CI or designee should complete and submit the Pregnancy Reporting Form to the Sponsor as soon as they are aware of the event using the dedicated email address [contact].

Any pregnancy that occurs in a participant or participant's partner during the trial should be followed to outcome. Follow up/outcome information should be provided to the Sponsor as soon as it becomes available. Any outcomes assessed as a SAE should be reported as per the SAE reporting procedure. The Pregnancy Reporting Form should also be submitted to the NICTU at the dedicated email address [contact].

